## 7.2. Immunogenicity

The incidence of anti-daratumumab antibodies along with the titer and incidence of neutralizing antibodies will be summarized for all subjects who receive at least 1 dose of Dara SC or Dara IV and have appropriate samples for detection of anti-daratumumab antibodies (i.e., subjects with at least 1 sample obtained after their first dose of daratumumab).

The incidence of anti-rHuPH20 antibodies along with the titer will be summarized for all subjects who receive a dose of Dara SC and have appropriate samples for detection of anti-rHuPH20 antibodies.

Subjects who are positive for anti-daratumumab or anti-rHuPH20 antibodies will be listed. A listing of subject status of anti-daratumumab or anti-rHuPH20 antibodies at any time during the study with daratumumab concentrations at the time of each immunogenicity sample will also be provided.

### 7.3. Pharmacokinetic/Pharmacodynamics Analyses

Pharmacokinetic/pharmacodynamic modeling may be performed, including exploring the relationship between serum concentrations of daratumumab and endpoints of clinical efficacy and safety. If performed, details and results of the analysis will be presented in a separate report.

## 8. BIOMARKER

Biomarker studies are designed to evaluate if there are any differences with Dara SC and Dara IV on biomarkers for daratumumab pharmacodynamics and mechanism of action. Samples for biomarker evaluations will be collected as specified in the protocol Time and Events Schedule.

The immunophenotyping analyses including the assessments of natural killer (NK) cells, T cells, and B cells in peripheral blood will be performed. The analyses for CD38+ myeloid-derived suppressor cells (MDSCs) and CD38+ regulatory T cells will also be performed.

Descriptive statistics for values and changes from baseline at each scheduled visit for absolute counts (cells/ $\mu$ l) of total NK cells and percent total NK cells (as a percentage of lymphocytes) in peripheral blood will be provided. The plots of absolute counts of total NK cells and percent NK cells in blood over time will also be provided. Similar analyses will be performed for CD8+ T cells, activated CD8+ T cells, CD3+ T cells, B cells, CD38+ myeloid-derived suppressor cells, and CD38+ regulatory T cells as well.

Further analysis of other biomarkers may be performed and the results may be presented in a separate report.

## 9. PATIENT-REPORTED OUTCOMES

The modified Cancer Therapy Satisfaction Questionnaire (modified-CTSQ) is a patient-reported outcome (PRO) measure to assess patient satisfaction of Dara SC compared with Dara IV in support of market access and payer request for patient-reported outcomes data.

The modified-CTSQ was adapted, with approval from the instrument developer, to contain 9 items specific to satisfaction with therapy and for comparison of IV with SC mode of administration. Each item asks about the most recent cancer therapy using a 5-point verbal rating scale (see Attachment 3). The modified-CTSQ asks about previous administration of daratumumab, not the current visit administration. To achieve unbiased assessments, the modified-CTSQ should be administered before the subject's clinical examination, the subject receives any tests or test results, and the subject's health, health data, or emotions are discussed.

The modified-CTSQ is a secondary endpoint, not part of the statistical hierarchy. Non-inferiority will not be analyzed for this endpoint. Type I error control was not applied to patient-reported outcome data.

### 9.1. Modified-CTSQ Scoring

For this study, the modified-CTSQ contains 1 multi-item domain (Satisfaction with Therapy [SWT]) and 2 single items (Thoughts about Cancer Therapy) as summarized in Table 4, each item has 5 response options coded as 1-5.

**Table 4: Modified-CTSQ Domain Structure and Scoring Information**

Modified-CTSQ Domain	Description of Items in Domain	Total # of Items	Minimum # of Completed Items Required to Score
Thoughts about Cancer Therapy (CT)	Q1: Worth taking even with side effects Q2: Think about stopping CT	2	No summary score
Satisfaction with Therapy	Q3: How worthwhile was CT Q4: Taking CT as difficult as expected Q5: Benefits meet expectations Q6: Were side effects as expected Q7: Satisfied with form of CT Q8: Satisfied with most recent CT Q9: Would you take this CT again	7	5

For most of the items, a higher coded number indicates a more positive response (e.g., 5 is the most positive response indicator and 1 is the least positive response indicator). However, for items Q2 (think about stopping CT) and Q4 (taking CT as difficult as expected), a higher coded number indicates a more negative response. For the analysis purpose, to ensure that a higher domain score is associated with a better response outcome and a lower domain score is associated with a worse response outcome, we need to reverse-code the response values for these two items Q2 and Q4. This is done by subtracting the initial (raw) response value from 6 for each of these 2 items. For example, we create 2 new variables Q2R and Q4R which contain reverse-coded response values for items Q2 and Q4:

$$Q2R = 6 - Q2;$$

$$Q4R = 6 - Q4;$$

To calculate the domain score for Satisfaction with Therapy (SWT), the minimum number of completed items is required, as shown in Table 4. If the number of completed items is greater than or equal to the minimum number of completed items required, the domain score is calculated using the following formula in general:

$$\text{Domain score} = \left[ \frac{\text{Sum of completed item responses}}{\text{Number of completed items}} - 1 \right] \times 100 / (\text{Maximum possible item response value} - \text{Minimum possible item response value})$$

However, if fewer items are completed than the minimum number indicated in Table 4, then the domain is not scored (i.e. a missing value is assigned).

Since the maximum possible item response value is 5 and the minimum possible response value is 1 for all modified-CTSQ items, a simpler way to represent the above formula for the modified-CTSQ SWT domain is: SWT domain score = (Mean of completed item responses – 1) × 25. For Q4 item, the reverse-coded response value Q4R is used in calculating SWT domain score.

For the modified-CTSQ SWT domain, a higher calculated domain score on a scale of 0 to 100 is a more positive indicator.

## 9.2. Analysis Method

Analysis of PRO data will be performed on ITT analysis set. For subjects with multiple records at the same visit, the closest one to the visit date will be selected as scheduled assessment, and others will be unscheduled assessments.

At each time point for analysis, the number and percentage of modified-CTSQ assessment forms that are expected, received and missing will be tabulated by treatment group. The missing PRO assessments are defined as the expected number of assessments for a particular visit minus the actual number of assessments received for that visit, the expected number of assessments per visit will be determined by subject-level study completion status.

For each modified-CTSQ item score and SWT domain score, descriptive statistics (n, mean, standard deviation, median, and range) will be provided for each time point by treatment group. The mean difference (with its 95% CI) of SWT domain score will be calculated and compared between treatment groups at each time point.

Line plot of mean scores with standard error over time will be displayed by treatment group for each individual item score and SWT domain score.

## 10. MEDICAL RESOURCE UTILIZATION

Medical resource utilization data associated with medical encounters due to IRRs or injection site reactions, primarily hospitalizations, outpatient visits and emergency room visits, will be collected in the eCRF by the investigator and study-site personnel for all subjects throughout the study.

Medical resource utilization will be descriptively summarized by treatment group. Frequencies of hospitalization, outpatient visits, type of hospitalization or outpatient visit, reasons for hospitalization or outpatient visit, durations of hospitalization or outpatient visit, types of adverse events if involved, blood product transfusions will be tabulated. The treatment-emergent adverse events leading to the hospitalization/outpatient visits and leading to on-study transfusions will also be summarized.

**ATTACHMENT 1: ADDITIONAL EXPLORATORY ANALYSIS TO SUPPORT HEMAR****1. DEFINITION OF SUBGROUPS**

Subgroup analyses will be performed using listed below to determine whether the treatment effect is consistent among subgroups. Analyses will be conducted for the ITT population and for the following subgroups:

- For subjects who reached CR/sCR as their best response
- For subjects who reached VGPR as their best response
- For subjects who reached PR as their best response
- For subjects who reached MR/SD as their best response
- For subjects who reached PD as their best response
- For subjects who reached MR or better as their best response (i.e. subjects with clinical benefit)
- For subjects who reached PR or better as their best response
- For subjects who reached VGPR or better as their best response

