### 5.2.2. Estimand

The primary estimand, the main clinical quantity of interest to be estimated in the study, is defined by the following 4 components:

- Population: subjects with relapsed or refractory multiple myeloma who have received at least 3 prior lines of therapy including a PI and an IMiD, or whose disease is double refractory to both a PI and an IMiD;
- Variable: overall response, which is defined as response if the best response is PR or better assessed at or prior to the start of subsequent anticancer therapy and non-response otherwise;
- Intercurrent event: Treatment discontinuation is considered as an intercurrent event for overall response and treatment policy strategy will be implement, i.e., disease assessments ignoring the treatment discontinuation will be implemented.
- Population-level summary: relative risk of overall response between two treatment groups.

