#### **5.3.7.2. Analysis Methods**

Analysis of DOR will be based on subjects who achieved a response of PR or better. Median DOR with 95% CI will be estimated based on the Kaplan-Meier method for each treatment group. The Kaplan-Meier curve for DOR will be plotted by treatment group.

No formal statistical comparison of DOR between the treatment groups will be made.

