**2. SUBGROUP ANALYZES**

Kaplan-Meier estimates will be used to estimate distribution of time to event by treatment arm based on all ITT population. Data will be calculated and summarized with descriptive statistics. The following time-to-event endpoints will be analyzed by pre-defined subgroups as defined in section 2.10 and in section 1, Appendix:

- PFS
- TNT
- OS
- DOR
- PFS2

In addition, as described in Sections 5.3.6 (TTR), 6.3.1 (IRR) and 9.2 (PRO), the following endpoints will be evaluated by pre-defined subgroups as defined in section 2.10 and in section 1, Appendix:

- TTR
- IRRs
- modified-CTSQ

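### SAP Attachment 1 judges consistency of the treatment effect within best-response groups, where a between-arm difference can appear or vanish without any difference in survival if the arms differ in who responds or how fast

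*SAP*

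**What the plan says.** SAP Attachment 1 is headed "ADDITIONAL EXPLORATORY ANALYSIS TO SUPPORT HEMAR". Its first section gives the aim of the subgroup analyses as "to determine whether the treatment effect is consistent among subgroups". The groups listed there are all best-response groups: CR/sCR, VGPR, PR, MR/SD, PD, and the cumulative groups MR or better, PR or better and VGPR or better. One entry, for example, reads "For subjects who reached PR or better as their best response".

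Its second section applies them: "The following time-to-event endpoints will be analyzed by pre-defined subgroups as defined in section 2.10 and in section 1, Appendix". The endpoints are PFS, TNT, OS, DOR and PFS2; TTR, IRRs and the modified-CTSQ are added after that. The method is "Kaplan-Meier estimates will be used to estimate distribution of time to event by treatment arm based on all ITT population", and "Data will be calculated and summarized with descriptive statistics".

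SAP Section 5.2.2 shows when best response is known. A subject counts as a "response if the best response is PR or better assessed at or prior to the start of subsequent anticancer therapy", so the classification builds up during follow-up. By contrast, every subgroup in SAP Section 2.10, Table 1, is a baseline characteristic. Attachment 1 contains no landmark, no time-dependent method and no caution about grouping on an outcome.

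**The concern.** A subgroup analysis of effect consistency relies on the arms being comparable within each subgroup. Randomisation secures that for baseline subgroups. It does not secure it for groups formed by response, which is itself a co-primary endpoint.

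Suppose SC turns more patients into responders. The extra responders tend to come from the middle of the prognosis range. They lower the average prognosis of SC responders, and their departure also lowers the average prognosis of SC non-responders. SC then looks worse in both groups although survival is the same overall. If SC converts fewer patients, both groups look better on SC. Either pattern looks like a consistent effect and is an artefact.

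Speed of response matters too. A responder must survive until the response, so the slower-responding arm has a longer built-in survival period among its responders.

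What is at stake is the reading of these exploratory outputs, not the trial's main conclusions.

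**Working it through.** The documents give no figure for Attachment 1, so there is none to reproduce. The check has three parts.

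**1. Simulation of OS within response groups**

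Inputs from the documents:
- 240 subjects per arm (SAP Section 1.5).
- IV response 29.2% (SAP Section 1.5).
- SC response 38%, from the 45-subject mix-and-deliver cohort (SAP Section 1.4), or 0.60 × 29.2% = 17.5%, the non-inferiority limit (SAP Section 1.3.1.1).
- Median OS 20.1 months (Protocol Section 1.2.1.1).
- Data collection to about 24 months after the last randomisation (Protocol Section 3.1).

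Assumptions:
- Latent prognosis U ~ N(0,1), with hazard λ·exp(−γU) and the same λ in both arms, set so that median OS is 20.1 months.
- Response if (U + e)/√2 > Φ⁻¹(1 − p), with e ~ N(0,1) and p the arm's response rate.
- γ = 0.5, 1.0 or 1.5, shown as a range because the documents do not give it.
- Follow-up of 24 to 36 months.

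Each scenario has 4,000 trials. Within each group the SC/IV estimate is HR = exp((O − E)/V), and a rejection is |(O − E)/√V| > 1.96. True OS is identical in every row.

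| Response IV v SC | ITT HR | HR, PR or better | HR, less than PR | Rejection, PR or better / less than PR |
|---|---|---|---|---|
| 29.2% v 29.2%, arms identical | 0.999–1.003 | 0.999–1.005 | 0.999–1.001 | 4.5–5.7% / 4.8–5.2% |
| Same, survival to response required (1–4 months, assumed) | 0.999–1.003 | 0.999–1.011 | 0.998–1.002 | 4.3–5.2% / 4.9–5.0% |
| 29.2% v 38% | 0.998–1.000 | 1.06–1.15 | 1.05–1.10 | 5.5–8.7% / 6.2–10.1% |
| 29.2% v 17.5% | 0.997–1.001 | 0.91–0.77 | 0.95–0.89 | 6.6–10.4% / 7.4–16.1% |

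In the last two rows the within-group HRs run in order from γ = 0.5 to γ = 1.5. With equal response rates but response at 1–3 months on SC and 1–6 months on IV (both windows assumed), the same model gives an HR of about 1.08 in responders.

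**2. Size against sampling error**

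Expected responders at 29.2% and 38% are 0.292 × 240 = 70 and 0.38 × 240 = 91, in total 161. If about half die (assume 80 deaths), SE(log HR) ≈ 2/√80 = 0.224. An HR of 1.06 would have a 95% CI of exp(0.058 ± 0.439) = 0.68 to 1.64. An HR of 1.15 would have exp(0.140 ± 0.439) = 0.74 to 1.78.

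**3. Checks from the definitions alone**

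- *PFS in the PD group.* SAP Section 5.3.1.1, Table 2, counts progression at or before subsequent therapy as the PFS event. A subject whose best response is PD has had that event, so the endpoint defines the group.
- *DOR and TTR in the MR/SD and PD groups.* SAP Section 5.3.7.2 states "Analysis of DOR will be based on subjects who achieved a response of PR or better", and SAP Section 5.3.6 limits TTR in the same way. These requested cells are empty.

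**The case against.** The strongest reply is that this is an exploratory attachment with Kaplan-Meier curves and descriptive statistics. It names no hazard ratio, log-rank test, interaction test or p-value; the hazard ratios above are a yardstick chosen for this check. The distortions are also small beside the sampling error in part 2, and outcome by depth of response is a legitimate thing to describe. All of this stands and keeps severity low. It does not rescue the stated aim, because curves by arm inside response groups do not answer a question about consistency of the treatment effect, with or without a p-value.

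A reader might infer several stronger points that the documents do not support:

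- *That the comparisons are biased even when the arms are identical.* They are not. Response then selects the same kind of patient in each arm, and survival to response acts equally on both; the first two table rows show this. What is distorted even then is responders versus non-responders (HR 0.84 from survival to response alone, with no prognostic link). That is a different contrast.
- *That Attachment 1 runs formal tests of consistency.* It does not.
- *That Attachment 1 introduces bias into DOR.* DOR is conditional on response by definition, and SAP Section 5.3.7.2 rules out a formal comparison.
- *That the outputs will drive a particular economic decision.* The SAP does not expand the abbreviation HEMAR or say how the results will be used.

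**Conclusion.** The point holds in a limited form. The stated purpose does not fit best-response groups, and following it could give an invalid reading of effect consistency for PFS, OS, TNT and PFS2. The condition is that SC and IV differ in who responds or how fast. The documents make that possible: 38% was seen in the early SC cohort against 29.2% on IV, and a ratio down to 0.60 counts as non-inferior.

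Only OS was simulated. With identical OS, the within-group hazard ratio shifts by about 5% to 15% at 29.2% versus 38%, and by about 5% to 23% in the other direction at 29.2% versus 17.5%. The sizes depend on the assumed link between prognosis and response; the direction follows from which arm responds more. The point about PFS in the PD group needs no assumption.

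The co-primary tests, the secondary hierarchy in SAP Section 5.1.1 and the ORR subgroup analysis in SAP Section 5.5 do not use these groups. Severity is low.

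**What to change.** - In Attachment 1, reserve the treatment-effect consistency purpose for the baseline subgroups of SAP Section 2.10.
- Keep the best-response groups, labelled as description of outcome by depth of response, with a sentence that no between-arm inference will be drawn within them because response is a post-randomisation outcome.
- If an association between response and later outcome is wanted, prespecify a landmark analysis (response status fixed at one stated time, follow-up counted from then) or fit response as a time-dependent covariate.
- Do not request DOR or TTR for the MR/SD and PD groups. Sections 5.3.6 and 5.3.7 already restrict both to responders, so nothing else changes there.

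The cost is a few sentences in an attachment, with no new data and no effect on sample size or on the confirmatory analyses. The landmark option loses subjects whose event comes before the landmark.

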**2. SUBGROUP ANALYZES**

Kaplan-Meier estimates will be used to estimate distribution of time to event by treatment arm based on all ITT population. Data will be calculated and summarized with descriptive statistics. The following time-to-event endpoints will be analyzed by pre-defined subgroups as defined in section 2.10 and in section 1, Appendix:

- PFS
- TNT
- OS
- DOR
- PFS2

In addition, as described in Sections 5.3.6 (TTR), 6.3.1 (IRR) and 9.2 (PRO), the following endpoints will be evaluated by pre-defined subgroups as defined in section 2.10 and in section 1, Appendix:

- TTR
- IRRs
- modified-CTSQ

**ATTACHMENT 3: MODIFIED CANCER THERAPY SATISFACTION QUESTIONNAIRE**

**Modified Cancer Therapy Satisfaction Questionnaire  
US English**

The following pages ask some questions about your cancer therapy (IV/SC). Within this questionnaire, “Cancer therapy (IV/SC)” refers to your current or most recent cancer therapy (including: IV therapy and subcutaneous therapy (SC)). Please read each question and answer as honestly as you can without the help of anyone. There are no right or wrong answers; the answers should be based on your own personal experiences.

**Your Thoughts about Cancer Therapy (IV/SC)**

The following statements ask you to share your thoughts about cancer therapy (IV/SC). Please answer each question below by checking the box that best represents your opinion (check only one box per question).

- In general, in the last four weeks, how often did you feel:**
- |  | Always  | Most of the time  | Sometimes  | Rarely  | Never  |
|--|---|---|--|---|--|
| 1. That cancer therapy (IV/SC) was worth taking even with the side effects?  |  5           |  4                     |  3              |  2           |  1          |
| 2. In general, in the last four weeks , how often did you think about stopping your cancer therapy (IV/SC)? |  5
Always |  4
Most of the time |  3
Sometimes |  2
Rarely |  1
Never |

**Satisfaction with Cancer Therapy (IV/SC)**

The following statements are about your satisfaction with your most recent cancer therapy (IV/SC). Please answer each question below by checking the box that best describes your level of satisfaction (check only one box per question).

3. **Overall**, how worthwhile was your cancer therapy (IV/SC)?
- |  |   |  |  |  |
|--|---|--|--|--|
|  5
Very worthwhile |  4
Quite worthwhile |  3
Moderately worthwhile |  2
A little worthwhile |  1
Not worthwhile at all |
|--|---|--|--|--|
4. **Overall**, was taking cancer therapy (IV/SC) as difficult as you expected?
- |   |   |  |   |   |
|---|---|--|---|---|
|  5
Much more difficult than I thought it would be |  4
Somewhat more difficult than I thought it would be |  3
As difficult as I thought it would be |  2
Somewhat easier than I thought it would be |  1
Much easier than I thought it would be |
|---|---|--|---|---|

5. **Overall**, how well did the **benefits** of cancer therapy (IV/SC) meet your expectations?

 5	 4	 3	 2	 1
Much better than my expectations	Somewhat better than my expectations	Met my expectations	Somewhat worse than my expectations	Much worse than my expectations

6. **Overall**, were the **side effects** of cancer therapy (IV/SC) as you expected?

 5	 4	 3	 2	 1
Much better than I expected	Somewhat better than I expected	Exactly as I expected	Somewhat worse than I expected	Much worse than I expected

7. How satisfied were you with the **form** of your cancer therapy (IV/SC)?

 5	 4	 3	 2	 1
Very satisfied	Satisfied	Neither satisfied nor dissatisfied	Dissatisfied	Very dissatisfied

8. **Overall**, how satisfied were you with your most recent cancer therapy (IV/SC)?

 5	 4	 3	 2	 1
Very satisfied	Satisfied	Neither satisfied nor dissatisfied	Dissatisfied	Very dissatisfied

9. Taking everything into consideration, if given the choice again, would you decide to take this cancer therapy treatment?

 5	 4	 3	 2	 1
Yes, definitely	Probably Yes	I don't know	Probably not	Definitely not

**Thank you.**
